### 6.1. Adverse Events (AE)

The analysis of AEs will be based on the medical dictionary for regulatory activities (MedDRA) coded terms as provided in the clinical database.

The safety endpoints (primary and secondary endpoints) are described in CTP Section 3.

#### 6.1.1. Definitions

The analysis of solicited AEs will be based on the overall assessment by the investigator. For unsolicited AEs, only the AEs starting within the 28-day period following vaccination will be presented in the safety tables, except for SAE, which will be captured and presented throughout the study. Unsolicited non-serious adverse events collected outside the 28-day period following the vaccination will be presented through listings.

By definition, all solicited AEs at the injection site (local) will be considered related to the study vaccine administration.

The severity of the AEs (solicited and unsolicited) will be classified as Mild (Grade 1), Moderate (Grade 2), Severe (grade 3) or Potentially Life Threatening (Grade 4). See CTP Section 10.2 and 10.3 for details on the criteria for the AE severity classification.

#### 6.1.2. Analysis of Adverse Events

Number and percentage of subjects with at least one particular AE (unsolicited/solicited) will be tabulated. Unsolicited AEs and SAEs will be summarized by System Organ Class and Preferred Term. Solicited AEs will be summarized by class (local, systemic) and preferred term.

For solicited AEs following tables will be provided: summary, by worst severity grade, at least grade 3, related (systemic only), time to onset (in days) and duration (in days) for most frequent events.

For solicited AEs, duration is defined as the number of days from the start of the event until resolution of the event. If the investigator reports multiple events of the same solicited AE in the reporting period (e.g., due to differences in their relationships to the study vaccine), duration will be derived from the onset date of the first event and the resolution date of the last event (date of resolution of last event – date of first onset + 1). The time to first onset is defined as (date of first onset – reference date + 1). The reference date is the start date of the regimen period.

For unsolicited AEs, the following tables will be provided: summary table (including SAE, fatal outcome), all AEs, most frequent AEs, grade 3, AE related study vaccine, SAE.

Listings and/or subject narratives will be provided as appropriate, for subjects who died, or experienced a severe or serious AE.

### **6.1.3. Phase allocation of Adverse Events**

As the analysis of solicited events will be based on the overall assessment of the investigator which is documented in the SDTM CE domain, ADaM datasets will be based on the CE domain. Solicited AEs will always be allocated to the post-dose period, they will not be attributed to the Screening Phase. Time is not considered while attributing solicited AEs to phases. For unsolicited AEs, the steps below will be followed.

#### **Step 1: Allocation of AEs to the phases**

Adverse events in the SDTM database are allocated to phases based on their start date/time.

- If the start date/time of an event falls between (or on) the start and stop date/time of a phase, the AE is attributed to that phase (emergent principle).
- In case of partial start or stop dates (i.e. time and/or day and/or month and/or year missing), the events are allocated to the phases using the available partial information on start and/or end date; no imputation will be done. If, for instance, for the AE start date only month and year are available, these data are compared to the month and year information of the phases. This rule may lead to multiplication of the event as a consequence of its assignment to multiple periods.
- In case of a completely missing start date, the event is allocated to the first active phase (post dose period), except if the end date of the AE falls before the start of the first active phase (post dose period).
- In case of a completely missing end date (for the calculation of duration), the date is imputed by the cut-off date of the analysis for subjects still ongoing in the study, and by the end date of the last phase for subjects who discontinued or completed the trial. The imputed end dates will not be shown in the data listings.

#### **Step 2: Combining overlapping/consecutive AEs**

Overlapping/consecutive events are defined as events of the same subject with the same preferred term which have at least 1 day overlap or for which the start date of an event is 1 day after the end date of the preceding event. Overlapping/consecutive events may or may not be combined into one AE, according to the following rules:

1. If an overlapping/consecutive event starts in a non-active period (screening or follow up phase), and is followed by an AE in a post-dose period (active period), they are allocated to their respective phases/periods and are considered as separate events.
2. If the overlapping/consecutive events start within the same period/phase, they are considered as one and the same AE. The individual events which contribute to this AE are retained as individual records in the ADaM database but are assigned the same onset, period, and total duration. All related attributes to the AE/phase/period should also be consistent with the new event.
3. If the overlapping/consecutive events start in both an active period followed by a non-active period, they are allocated to the active period only and are considered as one and the same AE. The individual events which contribute to this AE are retained as individual records in the ADaM database but are assigned the same onset, period, and total duration. All related attributes to the AE/phase/period should also be consistent with the new event.

Remarks:

- Events can only be combined into one and the same AE if their start and stop dates are known.
- In case the completely missing end date is imputed (for phase allocation), this date is also considered as a complete date.
- Time is not considered when determining overlap of events.

#### **6.1.4. Handling of Missing AE Data**

Missing data (severity grade, relationship) will not be imputed. Subjects for whom no event is reported by the investigator, will be considered as subjects without an event. An AE with a missing severity grade or relationship will be included in the tabulation of subjects with one or more AEs, but will be considered as ‘not reported’ for the tabulation of the severity grade or relationship. For example, an AE with missing severity will be considered as an AE reported for the analysis of any grade but will be considered as not reported for the analysis of grade 3.

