8.3.1. Time Period and Frequency for Collecting AE and SAE Information

AEs and special reporting situations, whether serious or nonserious, that are related to study procedures or that are related to noninvestigational sponsor products will be reported from the time a signed and dated ICF is obtained until the end of the study/early withdrawal.

Clinically relevant medical events not meeting the above criteria and occurring between signing of ICF and date of vaccination will be collected on the Medical History eCRF page as pre-existing conditions.

Any solicited local (injection site) or systemic AEs occurring during the 30-minute postvaccination observation period (or longer if deemed necessary by the investigator) will be documented by the study-site personnel following this observation period. Solicited AEs collected through a participant diary will be recorded from the time of vaccination until 7 days after vaccination.

All other unsolicited AEs and special reporting situations, whether serious or nonserious, will be reported from the time of vaccination until 28 days after vaccination. All AEs and SAEs leading to discontinuation of the study vaccination (regardless of the causal relationship) are to be reported from the moment of vaccination until completion of the participant's last study-related procedure, which may include contact for safety follow-up. All other SAEs (regardless of the causal relationship) are to be reported from the time of vaccination until the end of the study/early withdrawal.

All SAEs occurring during the study must be reported to the appropriate sponsor contact person by study-site personnel within 24 hours of their knowledge of the event. Information regarding SAEs will be transmitted to the sponsor using the SAE Form and Safety Report Form of the eCRF, which must be completed and reviewed by a physician from the study site, and transmitted to the sponsor within 24 hours. The initial and follow-up reports of an SAE should be transmitted electronically or by facsimile (fax).

The sponsor will evaluate any safety information that is spontaneously reported by an investigator beyond the time frame specified in the protocol.

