8.3.2. Method of Detecting AEs and SAEs

Care will be taken not to introduce bias when detecting AEs or SAEs. Open-ended and nonleading verbal questioning of the participant is the preferred method to inquire about AE occurrence.

Solicited AEs

Solicited AEs are used to assess the reactogenicity of the study vaccine and are predefined local (at the injection site) and systemic events for which the participant is specifically questioned and which are noted by participants in their participant diary.

After vaccination with study vaccine on Day 1, participants will remain under observation at the study site for a minimum of 30 minutes for presence of any acute reactions and solicited events, or longer if deemed necessary by the investigator. In addition, participants will record solicited signs and symptoms in the participant diary for 7 days after vaccination. All participants will be provided with the participant diary and instructions on how to complete the diary (Section 8). The study-site personnel will transcribe the information provided by the participant into the relevant sections of the eCRF. After review and verbal discussion of the initial participant diary entries with the participant, the investigator will complete his or her own assessment in the relevant sections of the eCRF. Once a solicited sign or symptom from the participant diary is considered to be of severity Grade 1 or above during the investigator's assessment, it will be recorded as a solicited AE.

Solicited Injection Site AEs

Participants will be asked to note in the participant diary occurrences of injection site pain/tenderness at the study vaccine injection site daily for 7 days after vaccination (day of vaccination and the subsequent 7 days). The extent (largest diameter) of any erythema and swelling at the injection site should be measured (using the ruler supplied) and recorded daily. The case definitions for solicited injection site events can be found in Gidudu et al.⁷ and Kohl et al.¹¹

Solicited Systemic AEs

Participants will be instructed on how to record daily body temperature using a thermometer provided for home use. Participants should record the body temperature (oral route preferred) in the participant diary in the evening of the day of vaccination, and then daily for the next 7 days

approximately at the same time each day. If more than one measurement is made on any given day, the highest body temperature of that day will be used in the eCRF.

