### 2.3.1. Full Analysis (FA) set

The FA set will include all participants who were randomized and received the study vaccine, regardless of the occurrence of protocol deviations. All safety and participant information analyses will be based on the FA set.

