### 4.2. Disposition Information

The number and percentage will be tabulated for subjects that were:

- Screened
- not randomized, not vaccinated
- not randomized but vaccinated
- randomized not vaccinated
- randomized and vaccinated (subjects in the FA set)
- in the PPI set

Number and percentage of subjects who discontinued the study together with the reason(s) for discontinuation will also be tabulated.

The number and percentage of subjects per study phase and period will also be tabulated.

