## 6. SAFETY

Continuous variables will be summarized using the following statistics, as appropriate: number of observations (N), arithmetic mean (mean), 95% confidence interval (CI) for the mean, standard deviation (SD), standard error (SE), median, quartiles (Q1 and Q3), minimum and maximum. Frequencies and percentages (to one decimal place) will be generated for categorical variables.

Safety data will be summarized per cohort, vaccine group and study phase. In addition, for a selection of tables, data of Cohorts 2 and 3 may be pooled over cohorts.

Safety data will be presented only for the active period or phase, except SAEs which will be presented in all phases in which they were reported. The analysis phases are defined in Section 2.1.1. Denominator for the percentages is the number of subjects in the considered analysis set and period/phase for a certain vaccine group (incidence per 100 subjects/period).

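### Solicited-AE tables count a vaccinated participant with no recorded solicited event and no investigator assessment after the Day 1 observation as having no event, and no planned output shows how many there are

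*SAP*

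**What the plan says.** Four SAP rules act together.

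- **Missing reports (SAP 6.1.4).** "Subjects for whom no event is reported by the investigator, will be considered as subjects without an event". The section sits under SAP 6.1, which covers solicited and unsolicited events. It does not require that an assessment took place. Its statement against imputation concerns only the grade and relationship of an event already reported.
- **Denominator (SAP 6).** "Denominator for the percentages is the number of subjects in the considered analysis set and period/phase for a certain vaccine group".
- **Analysis set (SAP 2.3.1).** "All safety and participant information analyses will be based on the FA set". That set is everyone randomized and vaccinated.
- **Period (SAP 2.1.1 and 6.1.3).** The post-dose period opens at vaccination, and "Solicited AEs will always be allocated to the post-dose period, they will not be attributed to the Screening Phase".

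On the source of the data, SAP 6.1.1 states "The analysis of solicited AEs will be based on the overall assessment by the investigator". Protocol 8.3.2 places that assessment after the diary has been reviewed: "After review and verbal discussion of the initial participant diary entries with the participant, the investigator will complete his or her own assessment". Site staff also document on Day 1 "Any solicited local (injection site) or systemic AEs occurring during the 30-minute postvaccination observation period" (Protocol 8.3.1).

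Solicited events over 7 days are a primary endpoint of Cohorts 2 and 3 and a secondary endpoint of Cohort 1 (Protocol 3).

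**The concern.** For unsolicited events, silence is a reasonable basis for recording no event. Solicited events are different: they are actively asked about, and they reach the AE tables through the investigator's assessment. A participant who was never assessed has missing data, and the SAP gives that participant the favourable value. It does not do so elsewhere. Missing immune responses are not imputed (SAP 5.2), and a laboratory or vital-sign abnormality with a missing baseline is always counted as emerging (SAP 6.2, 6.3).

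At stake are the absolute reactogenicity rates in Cohorts 2 and 3. These cohorts provide the first safety data above 1×10^11 vp and are meant to inform the upper release limit (Protocol 2.1, 4.3). Nothing is tested, so the tabulated percentages are the result. A reader of the report could not tell an assessed no-event participant from an unassessed one.

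**Working it through.** **Step 1: follow one participant through the rules.** Take someone who is vaccinated, has no solicited event noted during the Day 1 observation, and has no later investigator assessment.

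1. Randomized and vaccinated, so in the FA set (SAP 2.3.1).
2. In the post-dose period from the moment of vaccination (SAP 2.1.1), so in the denominator (SAP 6).
3. No event reported by the investigator, so a participant without an event (SAP 6.1.4).

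Neither document sets another denominator for solicited events, requires an assessment, or asks for a count of the unassessed.

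**Step 2: the nearest stated safety figure.** The point rests on no number in the plan, but the precision basis can be checked. With zero events, the 95% one-sided upper limit is 1 − 0.05^(1/N). For N = 25, 50 and 75 this gives 11.29%, 5.82% and 3.92%, matching Protocol Table 5 (11.3%, 5.8%, 3.9%). If 1 or 2 of 50 were unassessed, a zero-event row really rests on 49 or 48 participants, and the limit becomes 5.93% or 6.05%. For 1 or 2 of 25 it becomes 11.73% or 12.21%.

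**Step 3: size of the understatement.** Let N be the group size, m the number unassessed with no event recorded, and q their true event probability. Neither m nor q is in the documents, so both are assumptions.

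Expected understatement = q × m / N. It is zero if m = 0 and cannot be negative.

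| N | m | q = 20% | q = 80% |
|---|---|---|---|
| 50 (Groups 6, 7, 10) | 1 | 0.2×1/50 = 0.4 points | 0.8×1/50 = 1.6 points |
| 50 | 2 | 0.2×2/50 = 0.8 points | 0.8×2/50 = 3.2 points |
| 25 (Groups 8, 9, 11) | 1 | 0.2×1/25 = 0.8 points | 0.8×1/25 = 3.2 points |
| 25 | 2 | 0.2×2/25 = 1.6 points | 0.8×2/25 = 6.4 points |

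If missingness is unrelated to events (q = p), the expected reported rate is p(1 − m/N). At an assumed p = 50%:

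- N = 50: 49% (m = 1) or 48% (m = 2).
- N = 25: 48% (m = 1) or 46% (m = 2).

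For scale, the binomial standard error at p = 50% is √(0.25/50) = 7.1 points and √(0.25/25) = 10 points.

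**Step 4: contrasts between groups.** Assume true rates of 60% on active and 20% on placebo, a difference of 40 points.

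- Two of 25 unassessed on placebo only: 0.60 − 0.20×23/25 = 41.6 points.
- Two of 50 unassessed on active only: 0.60×48/50 − 0.20 = 37.6 points.

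A contrast can therefore move either way.

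**The case against.** The strongest reply is that few participants will be affected, and much of it stands.

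- **Recovery.** A missed diary review is done at the following visit (Protocol 8). An early exit within 7 days records solicited events (Protocol 1.3.2). Sites must try repeatedly to regain contact (Protocol 7.5), and the COVID-19 appendix calls for a safety interview at each contact.
- **Timing.** The DRC review at the end of Cohort 2 waits until every participant has completed Day 8 or discontinued (Protocol 4.1, 9.6), and Day 8 is the diary-review visit. The unassessed in that cohort should be mostly early discontinuers. In Cohort 3 the DRC review is tied only to the first 16 participants.
- **Visibility.** Discontinuations are tabulated, and "The number and percentage of subjects per study phase and period will also be tabulated" (SAP 4.2). Diary and on-site temperatures are tabulated separately (SAP 6.3), so fever does not depend wholly on the investigator's assessment.
- **Convention.** The rule is stated in advance, uses the whole vaccinated set, and serves a descriptive study.

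These safeguards reduce the number unassessed, but none sets an analysis rule for those who remain. The disposition tables do not show how many no-event participants still in the study were assessed, and SAP 4.3 tabulates only major deviations. The separate data presentation specifications were not available and might include such a count. The denominator and the missing-data rule are nevertheless fixed in the SAP.

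Two stronger readings are tempting. A reader might infer that everyone lost after vaccination is counted as event-free. The documents do not support that, because a solicited event recorded on Day 1 still counts. A reader might also infer a known bias in the dose comparison. Step 4 shows that the direction depends on where the unassessed fall, and the documents do not say.

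**Conclusion.** The point holds as a minor one. As written, the SAP turns an absent solicited-AE assessment into no event, for an endpoint that is primary in Cohorts 2 and 3. The rule can only lower an absolute rate or leave it unchanged, and the planned outputs described do not reveal how often it was applied.

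The size is assumed, not known. For 1 or 2 unassessed of 50 and a true event probability of 20% to 80% among them, the understatement is 0.4 to 3.2 points, well inside sampling error at that group size. If nobody is unassessed, nothing changes. The case for acting is that the remedy is cheap and makes the tables verifiable; the documents do not show that the safety conclusions would differ.

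**What to change.** 1. In SAP 6.1.4 and SAP 6, limit the no-report-means-no-event rule to unsolicited AEs and SAEs.
2. For each solicited-AE row, use as denominator the FA participants who either have an investigator assessment covering time after the Day 1 observation or have that event recorded at any time.
3. Report by group the number with no such assessment and the number whose assessment covers less than 7 days. The second count is needed because a participant seen only at an early exit would otherwise still pass as event-free for the whole week.
4. Show the full FA-denominator table as the lower bound, and a table counting the unassessed as events as the upper bound.
5. Record the departure in SAP 1.6, which now states no changes, because Protocol 9.3 and 9.4.3 base safety analyses on the full analysis set.

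**Worked example.** Suppose 24 of 48 assessed participants in a group of 50 had the event and none was recorded in the other 2. The main rate is 24/48 = 50%, with bounds 24/50 = 48% and 26/50 = 52%.

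The second clause of item 2 matters. If both unassessed participants had that event recorded on Day 1, a denominator of assessed participants alone would give 24/48 = 50%, below the 26/50 = 52% on the FA set, because it drops known reactions. With the clause, the main rate is (24+2)/(48+2) = 52%. The clause admits unassessed participants only when they had the event, so it leans slightly upward, but the main rate always lies between the two bounds.

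**Cost.** A few SAP sentences, one flag in the analysis dataset, and one or two extra tables. Denominators become slightly smaller and may differ by row. Rates are equal to or slightly less favourable than those on the FA set.

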#### **6.2. Clinical Laboratory Tests (Cohorts 2 and 3 only)**

Laboratory toxicity grades will be determined according to the FDA toxicity grading table (CTP Section 10.2). If toxicity grades are not defined for a test, the abnormalities (above/below normal range) will be determined according to the clinical laboratory normal ranges.

Emerging abnormalities will be tabulated by worst toxicity grade. An abnormality (toxicity grade or abnormality based on normal ranges) will be considered as emerging in a particular period if it is worse than the baseline value. If the baseline is missing, the abnormality is always considered emerging. A shift from ‘abnormally low’ at baseline to ‘abnormally high’ post baseline (or vice versa) is also emerging. In case a laboratory test result is censored (no numeric value is available, but only a verbatim term) then a numeric value will be imputed by a value exceeding the cut-off value with one unit. (i.e., for “ $<x$ ”, subtract 1 unit from  $x$ . For “ $>x$ ” add 1 unit to  $x$ . E.g.,  $<3.45$  is imputed with 3.44).

In determining toxicity grades and abnormalities based on normal ranges, the following rules apply:

- Worst grades/abnormalities are determined over the whole observational period for each trial phase separately, including all post-baseline measurements of that phase.
- The abnormalities ‘abnormally low’ and ‘abnormally high’ are considered equally important, i.e. if a subject has both an abnormally low and an abnormally high value in a post-baseline phase, both abnormalities are shown in the tables. (This means that the sum of the percentages can be more than 100%)
- The grading scale of some parameters in the grading table has gaps (zones where no toxicity grade definition exists). Laboratory results falling in these zones will be allocated to the adjacent worst-case grade.
- If a laboratory value falls within the grading as specified in the grading table but also within the local lab normal limits, the value is considered as normal.
- For the grading on hemoglobin changes from baseline, the corresponding actual value should be at least grade 1. Toxicity grades of the actual values and changes from baseline will be tabulated separately.
- Only the laboratory actual values will be used to determine the toxicity grades. For some parameters, extra clinical assessments are required to attribute a grade 4 toxicity (e.g., requiring hospitalization or dialysis), but these are not taken into account in this laboratory safety analysis.

For the grades, no distinction will be made between test results of samples obtained under fasting and under non-fasting conditions: if the normal range under fasting and non-fasting conditions differ, the normal range of the conditions (fasting/non-fasting) of scheduled visits as planned in the CTP will always be used, also for samples obtained under a different condition (e.g. samples of withdrawal visits).

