Postvaccination reactogenicity after administration of Ad26-based vaccines have consisted of mild to moderate adverse events (AEs), including local injection site reactions (most frequently injection site pain), and malaise, fatigue, headache, and myalgia. A trend towards an increase in the incidence of injection site pain and arthralgia, chills, fatigue, headache, malaise, myalgia, and nausea with an increase in Ad26 dose level was observed. There was no clear trend in the frequency of unsolicited AEs with increasing the Ad26 dose level. Transient decreases in neutrophil counts have been associated with adenovirus-based vaccines, and decrease in hemoglobin from baseline was the most frequent laboratory abnormality.¹

Risks Related to RSV preF Protein

RSV preF protein is being evaluated in the ongoing studies VAC18193RSV1004 and VAC18193RSV2001. To date, limited clinical data have shown an acceptable safety and reactogenicity profile.

Risks from Collection of Nasosorption Samples

Nasosorption sampling is more comfortable and less invasive than using a conventional swab (which may cause nose bleeds).

Risks from Blood Draws

As with all clinical studies requiring blood sampling, there are risks associated with venipuncture and multiple blood sample collection. Blood drawing may cause pain, tenderness, bruising, bleeding, dizziness, vaso-vagal response, syncope, and, rarely, infection at the site where the blood is taken. The total blood volume to be collected is considered to be an acceptable amount of blood over this time period from the population in this study (Section 4.2.1). Participants with contraindications to IM injections and blood draws (eg, bleeding disorders) will be excluded.

Participants with Immunosuppression/Reduced Immune Response

Participants with abnormal function of the immune system will be excluded from the study. Limited evidence indicates that inactivated vaccines (or nonreplicating viral vaccines) generally have the same safety profile in immunocompromised patients as in immunocompetent individuals. However, the magnitude, breadth, and persistence of the immune response to vaccination may be reduced or absent in immunocompromised persons.

Concomitant Vaccination

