** The clinical signs or symptoms associated with laboratory abnormalities might result in characterization of the laboratory abnormalities as potentially life-threatening (Grade 4). For example, a low sodium value that falls within a Grade 3 parameter (125-129 mEq/L) should be recorded as a Grade 4 hyponatremia event if the participant had a new seizure associated with the low sodium value.

***ULN is the upper limit of the normal range.

Hematology *	Mild (Grade 1)	Moderate (Grade 2)	Severe (Grade 3)	Potentially Life Threatening (Grade 4)
Hemoglobin (Female) - gm/dL	11.0 – 12.0	9.5 – 10.9	8.0 – 9.4	< 8.0
Hemoglobin (Female) change from baseline value - gm/dL	Any decrease – 1.5	1.6 – 2.0	2.1 – 5.0	> 5.0
Hemoglobin (Male) - gm/dL	12.5 – 13.5	10.5 – 12.4	8.5 – 10.4	< 8.5
Hemoglobin (Male) change from baseline value – gm/dL	Any decrease – 1.5	1.6 – 2.0	2.1 – 5.0	> 5.0
WBC Increase - cell/mm ³	10,800 – 15,000	15,001 – 20,000	20,001 – 25, 000	> 25,000
WBC Decrease - cell/mm ³	2,500 – 3,500	1,500 – 2,499	1,000 – 1,499	< 1,000
Lymphocytes Decrease - cell/mm ³	750 – 1,000	500 – 749	250 – 499	< 250
Neutrophils Decrease - cell/mm ³	1,500 – 2,000	1,000 – 1,499	500 – 999	< 500
Eosinophils - cell/mm ³	650 – 1500	1501 - 5000	> 5000	Hypereosinophilic
Platelets Decreased - cell/mm ³	125,000 – 140,000	100,000 – 124,000	25,000 – 99,000	< 25,000
PT – increase by factor (prothrombin time)	1.0 – 1.10 x ULN**	1.11 – 1.20 x ULN	1.21 – 1.25 x ULN	> 1.25 ULN
PTT – increase by factor (partial thromboplastin time)	1.0 – 1.2 x ULN	1.21 – 1.4 x ULN	1.41 – 1.5 x ULN	> 1.5 x ULN
Fibrinogen increase - mg/dL	400 – 500	501 – 600	> 600	--
Fibrinogen decrease - mg/dL	150 – 200	125 – 149	100 – 124	< 100 or associated with gross bleeding or disseminated intravascular coagulation (DIC)

* The laboratory values provided in the tables serve as guidelines and are dependent upon institutional normal parameters. Institutional normal reference ranges should be provided to demonstrate that they are appropriate.

** ULN is the upper limit of the normal range.

10.3. Appendix 3: Adverse Events: Definitions and Procedures for Recording, Evaluating, Follow-up, and Reporting

ADVERSE EVENT DEFINITIONS AND CLASSIFICATIONS

AE

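### SAP 6.2 leaves hemoglobin falls of Grade 2 or 3 size out of both grade tables when the final value is ungraded; one added table would restore them

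*SAP*

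**What the plan says.** Safety laboratory samples are taken only in Cohorts 2 and 3. The schedule (Protocol 1.3.2) has them at screening, on Day 1 before vaccination and on Day 8, so there is one planned post-vaccination value.

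Protocol Appendix 2 (Section 10.2) gives hemoglobin two kinds of row for each sex. The rows for the value itself read "Hemoglobin (Female) - gm/dL 11.0 – 12.0 9.5 – 10.9 8.0 – 9.4 < 8.0" and "Hemoglobin (Male) - gm/dL 12.5 – 13.5 10.5 – 12.4 8.5 – 10.4 < 8.5". The rows for the change read "Hemoglobin (Female) change from baseline value - gm/dL Any decrease – 1.5 1.6 – 2.0 2.1 – 5.0 > 5.0" and "Hemoglobin (Male) change from baseline value – gm/dL Any decrease – 1.5 1.6 – 2.0 2.1 – 5.0 > 5.0". The change rows carry no condition on the final value.

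SAP 6.2 adds one: "For the grading on hemoglobin changes from baseline, the corresponding actual value should be at least grade 1". It continues: "Toxicity grades of the actual values and changes from baseline will be tabulated separately". The same section treats a gradable value inside the laboratory's normal limits as normal, and tabulates only abnormalities worse than baseline.

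Protocol 8.2.3 and 9.4.3 already say that values inside the central laboratory's normal range are not graded; 8.2.3 adds that they are not recorded as AEs. Protocol 2.3.4, on earlier adenovirus-based vaccines, reports that "decrease in hemoglobin from baseline was the most frequent laboratory abnormality".

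**The concern.** The background signal is a change from baseline, and the Appendix 2 change rows are the part of the scale that measures a change. Under SAP 6.2 those rows are used only when the final value is already graded. A participant can lose more than 2 g/dL within about a week of vaccination and leave no mark in the graded laboratory tables.

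Cohorts 2 and 3 are where this matters, because they test doses above 1×10^11 vp, for which the protocol says it has no earlier safety data. SAP Section 3 applies the SAP's methods to the DRC analyses, so the DRC's graded tables would have the same gap, although the DRC may review all available safety data.

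Other routes do not reliably fill the gap. AE recording excludes in-range values. The introduction to SAP Section 6 offers means and confidence intervals for continuous variables only as appropriate, and 6.2 commits to no summary of hemoglobin change.

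**Working it through.** The plan states no figure on this point, so there is none to reproduce. The check applies the documents' own limits, with hemoglobin to one decimal.

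**Inputs** (Protocol Appendix 2, SAP 6.2, Protocol Table 2)
- Upper end of Grade 1 for the value: 13.5 g/dL (men), 12.0 g/dL (women). Lowest ungraded values: 13.6 and 12.1.
- Smallest fall of Grade 2 size: 1.6 g/dL. Smallest of Grade 3 size: 2.1 g/dL.
- Group sizes in Cohorts 2 and 3: 50 (Groups 6, 7, 10) and 25 (Groups 8, 9, 11).

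**Step 1. Lowest baseline from which a fall can go ungraded** = lowest ungraded value + size of fall.

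| | Grade 2 size | Grade 3 size |
|---|---|---|
| Men | 13.6 + 1.6 = 15.2 | 13.6 + 2.1 = 15.7 |
| Women | 12.1 + 1.6 = 13.7 | 12.1 + 2.1 = 14.2 |

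**Step 2. Largest ungraded fall from a given baseline** = baseline − lowest ungraded value.
- Man at 17.0: 17.0 − 13.6 = 3.4, so falls of 1.6 to 3.4 g/dL are ungraded.
- Woman at 15.0: 15.0 − 12.1 = 2.9, so falls of 1.6 to 2.9 g/dL are ungraded.

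Larger falls from these baselines reach Grade 1 on the value, and the change is then graded, unless the value is still inside the laboratory's normal limits.

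**Step 3. Effect of the normal-range rule.** Let L be the laboratory's lower normal limit. If L is below 13.6 (men) or 12.1 (women), values from L upward count as normal, and L replaces 13.6 or 12.1 in Steps 1 and 2. The baselines in the table then drop by the same amount. The documents do not give L.

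**Step 4. What the change table can still show.** A man going from 12.4 to 10.5 is Grade 2 on the value before and after. Judged by grade, he is not an emerging case in the value table, but his fall of 1.9 is Grade 2 in the change table. A woman going from 14.5 to 12.0 is at most Grade 1 on the value; her fall of 2.5 is Grade 3 on change, unless 12.0 is within normal limits.

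**Step 5. Weight of one participant.** 1/50 = 2 percentage points; 1/25 = 4 percentage points.

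**Step 6. Illustration on assumptions that are not in the documents.** Baseline mean 13.2–13.8 g/dL (women) or 14.3–15.0 (men), SD 1.1; mean fall 0.3–0.6, SD of change 0.5–0.8; normal distributions, simulated, with the normal-range rule ignored.
- Share of falls of at least 1.6 g/dL left ungraded: about 25–51% (women), 15–41% (men).
- Share of falls of at least 2.1 g/dL left ungraded: about 14–34% and 8–23%.
- If the condition were simply dropped, 62–86% of participants would have at least a Grade 1 change, because Grade 1 starts at any decrease.

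**The case against.** The strongest reply is that this is a stated convention and not a slip. Protocol 8.2.3 and 9.4.3 decline to grade in-range values, Appendix 2 footnotes its hematology limits as guidelines that depend on institutional ranges, and SAP 6.2 largely carries that approach over to the change rows. The condition also has a purpose: without it the Grade 1 column would fill with trivial decreases. Laboratory results are not a listed endpoint for Cohorts 2 and 3. The table specifications sit in a separate document that is not available here, and they may already include a summary of change.

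Most of this stands, and it keeps the point small. It does not remove the point. The normal-range sentences concern whether a value is graded; neither rules out describing a within-person change. Grade 1 noise is avoided by starting at 1.6 g/dL.

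Several stronger readings are tempting, and the documents do not support them:
- A reader might infer that the change table only repeats the value table. Step 4 shows that it can add both participants and severity.
- A reader might infer that every Grade 2 or 3 fall from a high-normal baseline is lost. Only falls ending above 13.5/12.0 g/dL or within normal limits are, and which baselines count as high-normal cannot be judged without the laboratory's range.
- A reader might infer that the plan sets out to compare hemoglobin across doses and that the rule biases the comparison. No such comparison is specified, and one rule applies to every group within a randomized cohort.
- A reader might infer that Grade 2–3 falls ending in range are the frequent event in the background data. Protocol 2.3.4 does not say how a decrease was counted or how large it was.

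**Conclusion.** The point holds as a loss of sensitivity. Falls of Grade 2 or Grade 3 size can go untabulated from the baselines in Step 1, or from lower ones if the laboratory's lower limit is below 13.6 or 12.1 g/dL. The thresholds rest only on the Appendix 2 limits and one-decimal reporting.

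How many participants are affected cannot be known from the documents. The ranges in Step 6 show that the share of larger falls missed could be material, but they depend on assumed baselines and changes.

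A reader might also see a contradiction between SAP and protocol, since SAP 1.6 declares no change from the planned analysis while 6.2 adds a condition absent from the Appendix 2 change rows. That goes too far: the protocol leaves technical detail to the SAP, and the condition is close to its normal-range convention. No primary result is affected. This is an inexpensive improvement to supportive safety reporting.

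**What to change.** Keep both current hemoglobin tables. Add one table to SAP 6.2 for Cohorts 2 and 3, by dose group and including placebo:
- number and percentage with a fall from baseline of at least 1.6 g/dL and of at least 2.1 g/dL, regardless of the final value;
- mean change from baseline with 95% CI.

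Include it in the DRC outputs as well. While editing 6.2, reconcile its reference to local laboratory limits with the protocol's central laboratory range.

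The cost is one table from data already collected. The drawback is that it will include some in-range falls of no clinical importance. The placebo groups (25 per cohort) put these in context, including any effect of the roughly 65 mL drawn on Day 1.
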